2.3.2. Known and Potential Risks

The short and long-term safety profile of selexipag has been established in PAH participants in study AC-065A302 (GRIPHON), conducted in 1156 participants, and is mainly characterized by prostacyclin-associated adverse events (AEs) linked with the mode of action of selexipag. Such AEs typically occur during the initial phase of individualized dose titration, and the susceptibility varies between individuals. Adverse drug reactions reflecting the mode of action of selexipag included: headache, diarrhea, nausea and vomiting, jaw pain, myalgia, pain in extremity, arthralgia, and flushing.

^a NCT02310672; EUDRACT: 2014-004066-20

Other AEs reported more frequently in the selexipag group compared with placebo group included hypotension, anemia, hyperthyroidism, nasopharyngitis, nasal congestion, decreased appetite, weight decreased, rash, urticaria, and erythema.

Hypotension was reported more frequently in the selexipag group than in the placebo group (5.0% and 3.1%, respectively). In the selexipag group, 9.7% of participants had systolic blood pressure (SBP) <90 mmHg on at least 1 occasion, compared with 6.7% in the placebo group. A decrease from baseline of >40 mmHg in SBP was reported for 2.3% and 3.0% of participants in the selexipag and placebo groups, respectively.

Hyperthyroidism was reported more frequently in the selexipag group compared with the placebo group. Corresponding laboratory changes were a small reduction in thyroid-stimulating hormone at most postbaseline visits.

Anemia was reported more frequently in the selexipag group, and a small reduction in hemoglobin was observed at most postbaseline visits.

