9.4.5. Safety Analyses

Safety analyses will be performed on the SS.

Adverse Events

A treatment-emergent AE is any AE from first dose up to 3 days after end of study intervention. The number and percentage of participants experiencing at least 1 treatment-emergent AE or SAE will be tabulated by:

- Medical Dictionary for Regulatory Activities system organ class and individual preferred term, in descending order of incidence.
- Frequency of participants with events coded with the same preferred term, in descending order of incidence.

Furthermore, treatment-emergent AEs and SAEs will be tabulated as described above by severity and relationship to study intervention. SAEs will be also tabulated up to 30 days after end of study intervention.

AEs leading to premature discontinuation of study intervention, AEs with an outcome of death, and AEs of special interest will be summarized as described above. The detailed list of AEs of special interest will be specified in the SAP.

AEs occurring during titration period will also be summarized separately.

Listings will be provided for all reported AEs, including SAEs. In addition, separate listings, as well as narratives, will be provided for SAEs, for AEs leading to premature discontinuation of study intervention, and for AEs with an outcome of death.

The following AEs will be listed only:

- AEs occurring prior to first study intervention dose
- Non-serious AEs occurring after EOT + 3 days
- SAEs occurring more than 30 days after discontinuation of study intervention

Clinical Laboratory Tests

Descriptive summary statistics by visit will be provided for observed values and absolute changes from baseline, in both hematology and clinical chemistry laboratory tests. In order to minimize missing data and to allow for out-of-window visits, all recorded assessments up to EOT + 3 days will be assigned to the most appropriate visit timepoint according to the best fitting time window for that assessment.

The sponsor's internal guidelines will be used for the definitions of marked abnormalities and for the standardization of numeric values obtained from different laboratories and/or using different normal ranges. Standard numeric laboratory variables will be transformed to standard units. All laboratory data transferred will be taken into account regardless of whether they correspond to scheduled (per protocol) or unscheduled assessments.

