### 5.6.2. Adverse Events

The verbatim terms used in the CRF by investigators to identify adverse events will be coded using the Medical Dictionary for Regulatory Activities (MedDRA). Any AE occurring at or after the initial administration of study intervention through the day of last dose plus 3 days is considered to be treatment-emergent. If the event occurs on the day of the initial administration of study intervention, and either event time or time of administration are missing, then the event will be assumed to be treatment emergent. If the event date is recorded as partial or completely missing, then the event will be considered to be treatment emergent unless it is known to be prior to the first administration of study intervention based on partial onset date or resolution date. All reported treatment-emergent adverse events will be included in the analysis. For each adverse event, the number and percentage of participants who experience at least 1 occurrence of the given event will be summarized.

Note: for participants who are entering another open-label clinical study with selexipag, safety information will be reported up to the last dose in RESTORE as the EOT visit will be combined with EOS visit. This is intended to avoid duplicate reporting of adverse events (AEs).

Summary tables will be provided for treatment-emergent adverse events by System Organ Class (SOC) and Preferred Term (PT):

- AEs
- Serious AEs (SAEs)

- AEs leading to discontinuation of study intervention
- AEs of COVID-19
- AEs by severity
- AEs by relationship to study intervention

SAEs will also be tabulated up to 30 days after end of study intervention or EOS whichever is first. In addition to the summary tables, listings will be provided for participants who:

- Had AEs
- Had SAEs
- Had AEs leading to discontinuation of study intervention
- Had AEs of special interest (AESI) (see [Appendix 8](#))

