## 6.8. Appendix 8 Adverse Events of Special Interest

The following adverse events of special interest will be used for selexipag. These are based on the important identified and potential risks in the latest Risk Management Plan and on-going discussion with Pharmacovigilance Risk Assessment Committee.

AE Special Interest Category
Anaemia
Bleeding events
Gastrointestinal disturbances denoting intestinal intussusception (manifested as ileus or obstruction)
Hyperthyroidism
Hypotension
Light-dependent non-melanoma skin malignancies
Major adverse cardiovascular events (MACE)
Medication errors
Ophthalmological effects associated to retinal vascular system
Pregnancy
Pulmonary venoocclusive disease associated with pulmonary oedema
Renal function impairment / acute renal failure
Prostacyclin associated reactions*

\*Prostacyclin associated reactions will be summarized separate from other AESIs

A specific file containing all preferred terms for each category as per last coding version will be maintained.

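### SAP 5.6.2 plans no titration-period adverse-event table and names AEs of special interest only under listings, although Protocol 9.4.5 commits to summarising both and the SAP declares neither change

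*SAP*

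**What the plan says.** **Protocol.** Section 9.4.5 first describes the standard AE table: number and percentage of participants with at least one treatment-emergent event, by MedDRA system organ class and preferred term. It then says of several groups of events: "AEs with an outcome of death, and AEs of special interest will be summarized as described above". It adds: "AEs occurring during titration period will also be summarized separately". The synopsis repeats both commitments. What 9.4.5 hands to the SAP is the content of the AESI list: "The detailed list of AEs of special interest will be specified in the SAP". AESIs are a secondary safety endpoint in Protocol Section 3 and again in SAP 1.1.

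**SAP.** Section 5.6.2 names six treatment-emergent tables by system organ class and preferred term: all AEs, serious AEs, AEs leading to discontinuation, COVID-19 AEs, AEs by severity and AEs by relationship. It also tabulates serious AEs up to 30 days after treatment, and 5.6.3 adds a table of deaths. AESIs come under "In addition to the summary tables, listings will be provided for participants who", with the entry "Had AEs of special interest (AESI" and a pointer to Appendix 8. Appendix 8 gives thirteen AESI categories, plans a file of preferred terms for each, and carries the footnote "Prostacyclin associated reactions will be summarized separate from other AESIs". Sections 5.1.4 and 5.1.5 define the start and end dates of the up-titration period, but the AE section does not use them.

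**The concern.** A programmer who follows SAP 5.6.2 will produce no titration-period AE table, and will find AESIs mentioned there only as a listing. The same programmer will then read a footnote in Appendix 8 that takes AESI summaries for granted. The SAP does not say which governs.

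Both summaries have a purpose in this trial. On prostacyclin-associated events, Protocol 2.3.2 says: "Such AEs typically occur during the initial phase of individualized dose titration". A titration-period table is the direct way to show tolerability in that phase. For AESIs, the natural result is the number of participants with at least one event in each category. That is the usual reading of a secondary safety endpoint defined by categories.

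At stake are fidelity to the protocol and a usable summary of two safety questions. The primary endpoint is unaffected.

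**Working it through.** The documents give no figure to reproduce, so the check is a comparison of texts, followed by a short illustration of what the missing tables would add.

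**1. Commitment against plan**

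| Item | Protocol 9.4.5 | SAP 5.6.2 | Elsewhere in the SAP |
|---|---|---|---|
| AESI summary | Committed, in the same form as other AEs | Not among the named tables; listing only | Presupposed by the Appendix 8 footnote |
| Titration-period AE summary | Committed, as a separate summary | Absent | Period dates in 5.1.4 and 5.1.5; no AE table anywhere |

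**2. Does early termination remove them?** SAP 5.1 restricts efficacy to listings but says that customary tables and listings will be produced for baseline characteristics and safety. Both missing items are safety summaries.

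**3. Does a declared change remove them?** SAP Appendix 2 declares an added normalised-RVSV endpoint, descriptive statistics only, no analysis on the full analysis or per-protocol sets, and no subgroup analysis. Both tables are descriptive, use the Safety Set and are not subgroups of participants. No declared change covers them.

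**4. What would an AESI table add to the main AE table?** The main table already counts participants for each preferred term, including AESI terms. It does not give category counts. A participant with two preferred terms in one category appears in two rows but counts once for the category, so adding rows can overstate the category count.

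**5. What would a titration table add?** SAP 5.6.2 uses one window, from first dose to last dose plus 3 days. Write p_t for the probability of at least one event in titration and p_m for that in maintenance. If the periods are assumed independent, overall incidence is 1 − (1 − p_t)(1 − p_m).

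- p_t = 40%, p_m = 20%: 1 − 0.60 × 0.80 = 52%.
- p_t = 20%, p_m = 40%: 1 − 0.80 × 0.60 = 52%.

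These percentages are assumed, not taken from the documents. They show only that one overall incidence cannot tell early events from late ones. Onset dates in the listings could, by manual count.

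**The case against.** **The list in 5.6.2 is not exhaustive.** This stands. The section tabulates serious AEs to 30 days after its six bullets, 5.6.3 adds deaths, and 5.1 promises customary safety tables in general terms. One cannot say that the SAP forbids further tables. But general wording in 5.1 is a weak basis for two specific protocol commitments when the section that specifies AE output names neither.

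**Appendix 8 is part of the SAP and already implies AESI summaries.** This also largely stands. A reader might infer that the SAP contradicts itself or has abandoned a secondary endpoint. The documents do not support that: a listing in one section and a summary presupposed in another are compatible. The AESI part is a failure of alignment. The titration-period part has no such support anywhere in the SAP.

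**Few participants, and everything is listed.** This is true and limits the consequence. SAP 5.3.2 and 5.5.7 cite the small numbers, and all AEs and AESIs are listed by participant. Small numbers are not, however, the SAP's reason for leaving out safety tables: it still tabulates COVID-19 AEs, severity and relationship in the same participants.

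**The period dates may serve another purpose.** SAP 5.6.1 reports exposure in the maintenance period, so the definitions in 5.1.4 to 5.1.7 do not by themselves show that an AE table was forgotten. That is fair. They show only that the table needs no new derivation.

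**Conclusion.** The concern holds as an undeclared departure from the protocol on the titration-period summary, and as an unclear specification of the AESI summary. It rests on the current text of both documents and on reading 5.6.2 as the section that specifies AE tables. The practical effect is modest: no inference is planned, the numbers are small, AESI preferred terms are counted in the main table, and the listings allow a manual count.

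A reader might go further and infer that overall AE incidence is biased, because titration is 84 of 364 planned treatment days (84/364 = 23%) and a larger share for anyone stopped early. The documents do not support that size of effect. The share describes exposure time, whereas the SAP tables count participants with at least one event, and neither document says when participants stopped. If events do cluster in titration, truncation after Week 12 may change that count little. With assumed p_t = 60% and p_m = 10% it is 1 − 0.40 × 0.90 = 64% over full follow-up, against 60% if stopped at Week 12. With 40% and 20% it is 52% against 40%. The direction is clear but the size depends wholly on the assumed values.

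**What to change.** Add two tables to the summary list in SAP 5.6.2, on the Safety Set:

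- Treatment-emergent AESIs by Appendix 8 category and preferred term, number and percentage of participants, with prostacyclin associated reactions shown separately. This brings 5.6.2 into line with the Appendix 8 footnote.
- Treatment-emergent AEs by system organ class and preferred term with onset in the up-titration period, using the dates in 5.1.4 and 5.1.5.

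If the sponsor prefers not to produce either table, Appendix 2 should say so and give the reason, and the Appendix 8 footnote should be brought into line.

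A matching maintenance-period table with participant-time would help interpretation, but the protocol does not promise it and it is optional.

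The cost is two small descriptive tables, likely sparse, built from AE onset dates, period dates and the preferred-term file that the SAP already plans. No new data are needed.

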### **5.6.3. Deaths**

Deaths will be displayed. Frequencies for the following parameters will be included in the summary table:

- Number of participants who died
- Cause of death.
- Relationship to study intervention (yes/no).

A listing of participants who died will be provided.

### **5.6.4. Additional Safety Assessments**

#### **5.6.4.1. Clinical Laboratory Tests**

Clinical laboratory tests will be displayed for the participants included in the safety analysis set.

Descriptive statistics (observed values and absolute changes from baseline) will be presented for all chemistry and hematology laboratory tests at scheduled time points. All recorded assessments up to EOT + 3 days will be assigned to the most appropriate visit time point according to the best fitting time window for that assessment.

Scatter plots (eDISH plot) of maximum treatment-emergent ALT and AST versus maximum treatment-emergent total bilirubin up to EOT + 3 days will be presented.

An abnormality (abnormality based on criteria defined in tables in Appendix 10, Section [6.10](#)) will be attributed to the baseline and post baseline values.

Post baseline abnormalities will be compared with their corresponding baseline result:

- Treatment-emergent (TE) will be concluded if the post baseline value is worse than the baseline value.
- If the post baseline value is above the upper limit and the baseline value is below the upper limit (e.g., Normal or Low), then the post baseline abnormality will be considered TE. The same applies to the post baseline value being below the lower limit with the baseline value being above the lower limit (e.g., Normal or High).
- If the baseline value is missing, a post baseline abnormality will always be considered as TE.

Treatment-emergent marked laboratory abnormalities (see Section 6.10) will be summarized for each laboratory variable for which marked abnormalities are defined providing their incidence and frequency.

All laboratory data will be listed together with derived marked abnormality flag. A separate listing of all laboratory data for the subjects with at least one marked abnormality value will be provided.

#### **5.6.4.2. Vital Signs and Physical Examination Findings**

Physical examination findings will be listed. Vital signs include height (cm), weight (kg), BMI (kg/m^2), pulse (beats/min), systolic blood pressure (mmHg) and diastolic blood pressure (mmHg). Observed values and absolute change from baseline will be summarized descriptively by timepoint.

#### **5.6.4.3. Electrocardiogram**

Not applicable.

#### **5.6.4.4. Other Safety Parameters**

Not applicable.

### **5.7. Other Analyses**

#### **5.7.1. Pharmacokinetics**

Not applicable.

#### **5.7.2. Immunogenicity**

Not applicable.

#### **5.7.3. Pharmacodynamics**

Not applicable.

#### **5.7.4. Pharmacokinetic/Pharmacodynamic Relationships**

Not applicable.

**5.7.5. Biomarkers**

Biomarker samples will be used to generate circulating marker data for computational analyses. These analyses are considered exploratory and the results will be reported separately from the CSR.

**5.7.6. Health Economics**

Not applicable.

**5.7.7. Other Variables and/or Parameters**

Not applicable.

**5.7.8. Definition of Subgroups**

Following study premature termination, no subgroup analysis will be performed.

**5.8. Interim Analyses**

Not applicable.

**5.8.1. Data Monitoring Committee (DMC) or Other Review Board**

Not applicable.

## 6. SUPPORTING DOCUMENTATION

### 6.1. Appendix 1 List of Abbreviations

4D	4-dimensional
6MWD	6-minute walking distance
6MWT	6-minute walking test
AE	adverse event
AESI	adverse event of special interest
ALT/SGPT	alanine aminotransferase
ANCOVA	analysis of covariance
AST/SGOT	aspartate aminotransferase
ATC	anatomic and therapeutic class
BDI	Borg dyspnea index
BMI	body mass index
CI	confidence interval
CRF	case report form
CSR	Clinical Study Report
CTCAE	Common Terminology Criteria for Adverse Events
DMC	Data Monitoring Committee
DPS	Data Presentation Specifications
Echo	Echocardiogram
ECG	electrocardiogram
eCRF	electronic case report form
EOS	end of study
EOT	end of treatment
EQ-5D	EuroQol 5-Dimension scale
FDA	Food and Drug Administration
IAP	image acquisition protocol
ICF	informed consent form
ICH	International Conference on Harmonisation
IMD	individual maintenance dose
IQ	interquartile
LV	left ventricle, left ventricular
LVEDV	left ventricular end diastolic volume
LVEF	left ventricular ejection fraction
LVESV	left ventricular end systolic volume
MedDRA	Medical Dictionary for Regulatory Activities
mPAP	mean pulmonary arterial pressure
MRI	magnetic resonance imaging
NT-proBNP	N-terminal-pro-hormone brain natriuretic peptide
PA	pulmonary artery
PAH	pulmonary arterial hypertension
PAWP	pulmonary artery wedge pressure
PI	principal investigator
PT	prothrombin time
PVR	pulmonary vascular resistance
RA	right atrium, right atrial
RHC	right heart catheterization
RV	right ventricle, right ventricular
RVEDV	right ventricular end diastolic volume
RVEF	right ventricular ejection fraction
RVESV	right ventricular end systolic volume
RVGLS	right ventricular global longitudinal strain
RVSV	right ventricular stroke volume
SAE	serious adverse event
SAP	Statistical Analysis Plan
SBP	systolic blood pressure

---

SD	standard deviation
SMQs	standardised MedDRA queries
SS	Safety set
TEAE	treatment-emergent adverse event
WHO	World Health Organization
WHO-DD	World Health Organization Drug Dictionary

**6.2. Appendix 2 Changes to Protocol-Planned Analyses**

- The number and percent (%) of patients achieving a normalized RVSV assessed by MRI at Week 26 and Week 52 was added as an exploratory endpoint.
- Following premature study termination, it is clarified that only descriptive statistics will be reported, no analysis will be performed using FAS/PP and no subgroup analysis will be performed.

### 6.3. Appendix 3 Demographics and Baseline Characteristics

The number of participants in each analysis set will be summarized and listed overall.

Tables 4 and 5 present a list of the demographic variables and baseline disease characteristics that will be summarized overall for the SS analysis set.

**Table 4: Demographic Variables**

Continuous Variables:	Summary Type
Age (years)	Descriptive statistics (N, mean, standard deviation [SD], median and range [minimum and maximum], and IQ range).
Weight (kg)	
Height (cm)	
Body Mass Index (BMI) (kg/m  )	
Categorical Variables	
Age (18-<25 years, 25-<51 years, 51-<65 years and >=65 years)	
Sex (male, female, undifferentiated)	
Race a (American Indian or Alaska Native, Asian, Black or African American, Native Hawaiian or other Pacific Islander, White, Multiple)	Frequency distribution with the number and percentage of participants in each category.
Ethnicity (Hispanic or Latino, not Hispanic or Latino)	

a If multiple race categories are indicated, the Race is recorded as 'Multiple'

**Table 5: Baseline disease characteristics**

Continuous Variables:	Summary Type
Time since PAH diagnosis (months)	Descriptive statistics (N, mean, standard deviation [SD], median and range [minimum and maximum], and IQ range).
6MWD (m)	
BDI score (pre-walk, post-walk and difference pre-post)	
NT-proBNP (ng/L)	
Categorical Variables	
PAH Etiology	Frequency distribution with the number and percentage of participants in each category.
WHO FC (II, III)	
Naïve to PH therapies (yes, no)*	

\* Naïve to PH therapies participants are participants without any of the PAH-specific therapies listed in Section 6.9 (Appendix 9) taken as concomitant at baseline (see Section 6.5 for definition of concomitant medication at baseline)

For each subject time since PAH diagnosis (months) will be derived as:

$$(\text{Date of Day 1} - \text{date of diagnosis} + 1) / 30.4375.$$

Demographics and baseline characteristics will also be listed on the SS.

#### **6.4. Appendix 4 Protocol Deviations**

In general, major protocol deviations may have the potential to impact participants' rights, safety or well-being, or the integrity and/or result of the clinical study. Participants with major protocol deviations will be identified prior to database lock and the participants with major protocol deviations will be summarized by category.

See TV-FRM-04718 "Major Protocol Deviation Criteria" for detailed definitions of major protocol deviations.

A specific listing will be provided for major protocol deviations by region and site.

## **6.5. Appendix 5 Prior and Concomitant Medications**

Prior and Concomitant medications will be coded using the last available version of World Health Organization Drug Dictionary (WHO-DD). Prior medications are defined as any therapy used before the day of first dose (partial or complete) of study intervention.

**Concomitant medications** are defined as any therapy used on or after the same day as the first dose of study intervention, including those that started before the first dose of study intervention.

**Concomitant medication at baseline** is any medication taken at the same day of the first dose of study intervention (see Section [5.1.3](#)).

Summaries of concomitant medications will be presented by ATC class and PT on the SS. The proportion of participants who receive each concomitant medication will be summarized as well as the proportion of participants who receive at least 1 concomitant medication.

In addition, **concomitant medications of special interest** (PAH-specific) will be presented on the SS. See Appendix 9 (Section [6.9](#)) for list of medications in PAH-specific category.

In addition, summaries of concomitant medications of special interest at baseline will be presented by ATC class and PT on the SS in the same way.

Prior medications will be summarized by ATC term (highest available level) on the SS.

All prior and concomitant medications will also be listed, with flags for PAH-specific ones and for concomitant at baseline ones.

